6.2. General Considerations

This plan describes *a priori* statistical analyses for efficacy, health outcomes, and safety that will be performed.

Statistical analysis of this study will be the responsibility of Eli Lilly and Company (Lilly). The statistical analyses will be performed using SAS® Version 9.4 or higher.

Not all displays described in this SAP will necessarily be included in the clinical study report (CSR). Not all displays will necessarily be created as a “static” display. Some may be incorporated into interactive display tools instead of or in addition to a static display. Any display described in this SAP and not included in the CSR will be available upon request.

Statistical tests of treatment effects and CIs will be performed at a 2-sided significance level of 0.05, unless otherwise stated (e.g., graphical multiple testing strategy in Section 6.6).

Data collected at early termination visits will be mapped to the closest scheduled visit number for that patient if it falls within the visit window as discussed in Section 6.2.2. For by-visit summaries, only visits in which a measure was scheduled to be collected will be summarized. Any unscheduled visit data will be included at the patient-level listings. However, the data will still be used in other analyses, including shift analyses for safety analytes, change from baseline using modified last observation carried forward (mLOCF) for efficacy analyses, and other categorical analyses including safety.

6.2.1. Analysis Populations

Intent-to-treat (ITT) population: The ITT population analysis set is defined as all randomized patients.

Per-protocol Set (PPS): PP subset of the ITT analysis set will include those patients who do not have any significant or important protocol violations. Qualifications for and identification of significant or important protocol violations will be determined while the study remains blinded, prior to database lock.

Follow-up population: The follow-up population is defined as patients who entered the follow-up period.

Unless otherwise specified, the efficacy and health outcome analyses will be conducted on the ITT population (Gillings and Koch 1991), which seeks to preserve the benefits of randomization and avoid selection bias. Patients will be analyzed according to the treatment to which they were randomized. In addition, the analyses of primary and key secondary endpoints will be repeated using the PPS population.

Safety population: The safety population is defined as all randomized patients who receive at least 1 dose of investigational product and who did not discontinue from the study for the reason 'Lost to Follow-up' at the first postbaseline visit.

Safety analyses will be performed using the safety population. Patients will be analyzed according to the treatment regimen to which they were assigned. Analyses of the safety endpoints, many of which are incidence based, will include all patients in the safety population, unless specifically stated otherwise.

In the rare situation where a patient is Lost to Follow-up at the first postbaseline visit, but some safety data exists (e.g., unscheduled laboratory assessments) after first dose of study drug, a listing of the data or a patient profile will be provided, when requested.

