6.14. Safety Analyses

The general methods used to summarize safety data, including the definition of baseline value are described in Section 6.2.

Safety analyses will include data before and after rescue, unless otherwise stated, and patients will be analyzed according to the investigational product to which they were randomized at Visit 2. A sensitivity approach to the safety analyses will use data censored at last dose of the study drug for patients rescued to systemic therapy. These analyses will be conducted for treatment-emergent adverse events (TEAEs), serious adverse events (SAEs), AEs leading to permanent study drug discontinuation and special topics excluding deaths and malignancies. Additional analyses may be conducted using data after rescue to systemic therapy for some safety topics such as systemic TEAEs, and SAEs. Safety analyses will take place using the safety population defined in Section 6.2.1.

Safety topics that will be addressed include the following: AEs, clinical laboratory evaluations, vital signs and physical characteristics, Columbia Suicide Severity Rating Scale (C-SSRS), the Self-Harm Supplement Form, safety in special groups and circumstances, including adverse events of special interest (AESI) (see Section 6.14.5), and investigational product interruptions.

Unless otherwise specified, by-visit summaries will include planned on-treatment visits. For tables that summarize events (such as AEs, categorical lab abnormalities, shift to maximum value), post-last dose follow-up data will be included. Follow-up data is defined as all data occurring up to 30 days (planned maximum follow-up time) after last dose of treatment including rescue, regardless of study period. Listings will include all safety data.

For selected safety assessments other than events, descriptive statistics may be presented for the last measure observed during post-treatment follow-up (up to 30 days after the last dose of treatment including rescue, regardless of study period).

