6.14.1. Extent of Exposure

Duration of exposure (in days) will be calculated as follows:

- Duration of exposure to investigational product (including exposure after the initiation of rescue therapy): *date of last dose of study drug including rescue – date of first dose of study drug + 1.*

Last dose of study drug including rescue is calculated as last date on study drug. For patients discontinuing study drug or study due to the reason 'Lost to Follow-up', the duration of exposure is calculated as *date of second last visit - date of first dose of study drug + 1.*

Total patient-years (PY) of exposure to study drug will be reported for each treatment group for overall duration of exposure. Descriptive statistics will be provided for patient-days of exposure and the frequency of patients falling into different exposure ranges in addition to cumulative exposures will be summarized.

Exposure ranges will be summarized as follows:

- ≥ 28 days, ≥ 56 days, ≥ 84 days, and ≥ 112 days
- > 0 to < 28 days, ≥ 28 days to < 56 days, ≥ 56 days to < 84 days, ≥ 84 days to < 112 days, and ≥ 112 days

Overall exposure for a treatment group will be summarized in total PY which is calculated according to the following formula:

- $Exposure\ in\ PYE = \text{sum of duration of exposure in days} / 365.25$

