6.14.2. Adverse Events

Adverse events are recorded in the eCRFs. Each AE will be coded to system organ class (SOC) and PT using the Medical Dictionary for Regulatory Activities (MedDRA) version that is current at the time of database lock. Severity of AEs is recorded as mild, moderate, or severe.

A TEAE is defined as an event that either first occurred or worsened in severity after the first dose of study treatment and on or prior to the last visit date during the analysis period. The analysis period is defined as the treatment period plus 30 days off-drug follow-up time.

Adverse events are classified based upon the MedDRA PT. The MedDRA Lowest Level Term (LLT) will be used in defining which events are treatment-emergent. The maximum severity for each LLT during the baseline period up to first dose of the study medication will be used as baseline. If an event with missing severity is preexisting during the baseline period, and persists during the treatment period, then the baseline severity will be considered mild for determining treatment-emergence (that is, the event is treatment-emergent if the severity is moderate or severe postbaseline and not treatment-emergent if the severity is mild postbaseline). If an event occurring postbaseline has a missing severity, then the event is considered treatment-emergent unless the baseline is severe, in which case the event is not treatment-emergent. The day and time for events where onset is on the day of the first dose of study treatment will both be used to distinguish between pretreatment and posttreatment to derive treatment-emergence. Should there be insufficient data for AE start date to make this comparison (for example, the AE start year is the same as the treatment start year, but the AE start month and day are missing), the AE will be considered treatment-emergent.

In general, summaries will include the number of patients in the safety population (N), frequency of patients experiencing the event (n), and relative frequency (that is, percentage; $n/N * 100$). For any events that are gender-specific based on the displayed PT, the denominator used to compute the percentage will only include patients from the appropriate gender.

For events of special interest, a more robust incidence rate, IR per 100 patient-years of observation (PYO) may be provided. Patient-years of observation will be calculated as the sum

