of all patient observation time in the treatment group. For a patient with an event, the observation time will be censored at the event date; for a patient without the event, the observation time will be counted until the end of the analysis period.

PYO will be calculated as follows:

$$PYO = \sum_{pt \ w \ event} \frac{event \ start \ date - first \ trt \ dose \ date + 1}{365.25} + \sum_{pt \ w/o \ event} \frac{last \ observation \ date - first \ trt \ dose \ date + 1}{365.25}$$

IR will be calculated as follows:

$$IR = \frac{number \ of \ patients \ with \ event}{PYO} \times 100$$

For each IR provided, a Poisson Distribution 95% CI will be calculated. Treatment group comparisons will be provided based on the incidence rate difference (IRD) together with its 95% CI.

In an overview table, the number and percentage of patients in the safety population who experienced death, an SAE, any TEAE, discontinuation from the study due to an AE, permanent discontinuation from study drug due to an AE, or a severe TEAE will be summarized by treatment group.

The number and percentage of patients with TEAEs will be summarized by treatment group in 2 formats:

- by MedDRA PT nested within SOC with decreasing frequency in SOC, and events ordered within each SOC by decreasing frequency in the baricitinib 4-mg group;
- by MedDRA PT with events ordered by decreasing frequency in the baricitinib 4-mg group.

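### The safety population leaves out dosed patients who are lost to follow-up at the first postbaseline visit, so their post-dose events drop out of the summaries run on that set

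*SAP*

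**What the plan says.** SAP Section 6.2.1 starts from the usual definition: "The safety population is defined as all randomized patients who receive at least 1 dose of investigational product". It then adds a second condition, that the patient must be one "who did not discontinue from the study for the reason 'Lost to Follow-up' at the first postbaseline visit".

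The set is used widely. Section 6.14 states: "Safety analyses will take place using the safety population defined in Section 6.2.1". Section 6.14.2 takes it as the denominator N for adverse event summaries, and its overview table reports "the number and percentage of patients in the safety population who experienced death, an SAE, any TEAE", among other categories. Section 6.2.1 leaves room for exceptions: analyses of safety endpoints "will include all patients in the safety population, unless specifically stated otherwise".

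The same section accepts that an excluded patient can have safety data recorded after the first dose, and calls this rare. For such a patient, "a listing of the data or a patient profile will be provided, when requested".

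**The concern.** A safety set should contain everyone exposed to study drug. Here a patient who took study drug and then stopped attending is removed because of a post-dose outcome. Early disappearance can follow an early adverse effect, so the rule may select against the patients in whom early harm would show, and it need not act equally in all arms.

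The SAP also foresees the case in which post-dose data exist for such a patient, and still keeps those data out of the incidence tables. That sits awkwardly with its own handling of unscheduled records. Section 6.2 says unscheduled data feed the categorical safety analyses, and Section 6.14.3 counts unplanned measurements in the treatment-emergent high/low laboratory analysis. The SAP's example of data an excluded patient might have, an unscheduled laboratory result, is a record of that kind.

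At stake is the completeness of the counts for rare serious events, where one patient can be an arm's only case.

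**Working it through.** The SAP gives no figure for the number of patients excluded, so there is none to reproduce. The check traces the definition through the safety sections and then shows the scale under stated assumptions.

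**Inputs.** From the SAP: 120 patients in each baricitinib arm and 240 on placebo (Section 5.1); screening 8 to 35 days before Week 0 (Section 5.1); first postbaseline visit at Week 1, Visit 3 (Section 6.2.2); common-event threshold of 2% in any group (Section 6.14.2.1); Fisher's exact test for adverse event proportions (Section 6.2.3). Assumed: 1% to 3% of patients lost by the first postbaseline visit, and the event counts below.

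**1. Where the exclusion takes effect.** Incidence is n/N with N the safety population (Section 6.14.2), so an excluded patient leaves both n and N. Section 6.14.5.10 says the malignancy summaries take all cases in the study database. That sentence is about the gap after last dose and does not expressly override the population, so it is a possible exception only.

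**2. Patients removed.**
- Active arm: 1% to 3% of 120 = 1.2 to 3.6, about 1 to 4 patients.
- Placebo: 1% to 3% of 240 = 2.4 to 7.2, about 2 to 7 patients.

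Event counts change only for those of these patients who also have a recorded post-dose event, which will be fewer.

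**3. Effect on a rare event in an active arm.**
- One case, in the excluded patient: 1/120 = 0.83% becomes 0/119 = 0%.
- Three cases, one of them excluded: 3/120 = 2.50% becomes 2/119 = 1.68%. This is below the 2% threshold, so the term leaves the common-event table unless another arm meets it.
- Against an assumed 0/240 on placebo, Fisher's exact p goes from 0.036 (3/120) to 0.109 (2/119). This is a constructed case, not a forecast.

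**4. Effect when the excluded patients had no event.** With three event-free patients removed, 3/120 = 2.50% becomes 3/117 = 2.56%. The reported percentage rises slightly.

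**5. The exposure rule in Section 6.14.1.** It reads: "For patients discontinuing study drug or study due to the reason 'Lost to Follow-up', the duration of exposure is calculated as" the date of the second-to-last visit minus the date of first dose, plus one. For a patient lost at Visit 3:
- Visit 3 recorded as the last visit: the second-to-last is Visit 2, the expected day of first dose, giving 0 + 1 = 1 day.
- Visit 2 recorded as the last visit: taking screening as the second-to-last, −8 + 1 = −7 days to −35 + 1 = −34 days.

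The rule therefore gives a minimal or impossible duration for exactly these patients.

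**6. The treatment-emergent definition in Section 6.14.2.** An event must occur no later than the last visit date in the analysis period. If Visit 2 is the last visit, a later recorded event could fail this test even after the patient is put back in the set.

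**The case against.** The exclusion is prespecified, disclosed and identical across arms. It is also narrow. It acts only on one recorded reason at one visit, so a patient whose recorded reason is an adverse event or death stays in. The SAP calls post-dose data in such patients rare. Patients with essentially no follow-up add little, and counting them as event-free dilutes incidence a little. Many would be missing from the laboratory displays under either definition, because the box plots need a postbaseline visit and leave out unplanned values (Section 6.14.3), and the hepatic tables need a postbaseline value (Section 6.14.5.1).

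These arguments limit the size of the point but do not remove it. Being rare and prespecified does not justify omitting a known post-dose event from an incidence table.

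A reader might infer more than the SAP supports, in four ways:

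- *That the events vanish altogether, or from every table.* Section 6.14 says listings cover all safety data. Section 6.14.2.2 lists all serious events, and deaths whenever they occur. Sections 6.14.5.7 and 6.14.5.8 list events sent for adjudication. None of these depends on a request, although a listing does not restore a patient to n or N. Malignancies may be exempt.
- *That the rule can only lower reported rates.* It can only lower numerators; percentages can move either way, as step 4 shows.
- *That the exposure rule proves nothing stands in the way of including these patients.* Step 5 shows that the rule breaks down for them.
- *That loss differs by arm.* This is possible, but nothing in the SAP shows it.

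**Conclusion.** The point holds in limited form. The safety population is conditioned on a post-dose outcome, and recorded post-dose events in patients lost at the first postbaseline visit are left out of the numerators and denominators of the summaries run on that set. The number affected is not given and is probably small. The 1% to 3% used above is an assumption, and the event counts are illustrations. Common event rates would barely change. The practical risk is to rare events, where one excluded case is 0.83% of an active arm and could be the only one. No direction of bias in percentages, and no imbalance between arms, is established. The SAP gives no reason for the exclusion, and the remedy is small, so the change is worth making.

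**What to change.** Define the safety population in Section 6.2.1 as all randomized patients who receive at least one dose of investigational product, and delete the lost-to-follow-up condition. If consistency with other studies in the programme is wanted, keep the present set as a sensitivity set.

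Make two matching edits:

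- Section 6.14.1: amend the exposure rule for patients lost to follow-up so that it gives a valid duration when the loss occurs at the first postbaseline visit.
- Section 6.14.2: word the last-visit limit in the treatment-emergent definition so that recorded post-dose events in these patients are kept.

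If the present definition has to stay, the least that should change is to replace the on-request listing with a mandatory tabulation, by arm, of the excluded patients and their events.

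The cost is a few SAP sentences rather than one. A few patients with very little follow-up will enter the denominators, and the set will differ slightly from any programme convention.

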6.2.2. Definition of Baseline and Postbaseline Measures

The baseline value for efficacy and health outcomes variables measured at scheduled visits is defined as the last non-missing measurement on or prior to the date of first study drug administration (expected at Week 0, Visit 2).

The baseline value for the daily diary assessments (Itch NRS, ADSS, Skin Pain NRS, PGI-S-AD) and for the actigraphy analyses period is the mean of the non-missing assessments in the 7 days prior to the date of first study drug administration (expected at Week 0, Visit 2).

If there are less than 4 non-missing assessments in the baseline diary window, the interval lower bound can be extended up to 7 additional days, one day at a time, to obtain the most recent 4 non-missing values. If there are not at least 4 non-missing assessments in the baseline period, the baseline mean is missing.

The baseline value for actigraphy assessments is the mean of the non-missing assessments in the 7 days prior to the date and time of first study drug administration. The baseline mean for actigraphy variables require there be at least 4 non-missing measurements occurring in at least 4 separate 24-hour increments in the 7 days prior to the date and time of first study drug administration. If this condition is not satisfied, an expanded window of up to 14 days (336 hours) prior to first study drug administration may be utilized in order to obtain the most recent 4 non-missing measurements, occurring in 4 separate 24-hour increments. If there are not at least 4 non-missing assessments collected in the baseline period, the baseline mean will be designated as missing. Other definitions of baseline value, such as the last measurement on or prior to rescue, may be used to conduct additional supporting analyses.

Baseline for the safety analyses is defined as the last non-missing scheduled (planned) measurement on or prior to the date of first study drug administration for continuous measures by-visit analyses and non-missing measurements on or prior to the date of first study drug administration for all other analyses.

Postbaseline measurements are collected after study drug administration through Week 16 (Visit 8) or early discontinuation visit. Efficacy data collected at scheduled visits (e.g., eCOA, ClinRO) will be used in all analyses unless it is missing. If an assessment is missing at a scheduled visit, an unscheduled post-baseline assessment can be used provided it falls within the window interval as follows: a ± 2 day window is used for Visit 3 (Week 1), Visit 4 (Week 2), and Visit 5 (Week 4); and a ± 4 day window is used to Visit 6 (Week 8), Visit 7 (Week 12), and Visit 8 (Week 16). If there is more than 1 unscheduled visit within the defined visit window and no scheduled visit assessment is available, the unscheduled visit closest to the scheduled visit date will be used. If two unscheduled visits of equal distance are available, then the latter of the two will be used.

Postbaseline daily diary endpoints will be the mean of weekly visit windows (diary windows) anchored on day of first dose (Day 1) and day of Week 16 scheduled visit. Weeks 1-14 are defined as follows:

Week	Days
1	1-7
2	8-14
3	15-21
4	22-28
5	29-35
6	36-42
7	43-49
8	50-56
9	57-63
10	64-70
11	71-77
12	78-84
13	85-91
14	92-98

The Week 16 diary window is the 7 days prior to the scheduled Week 16 visit. If there is no Week 16 scheduled visit, the 7 days prior to the last visit (whether scheduled or unscheduled)

occurring after Day 105 constitutes the Week 16 diary window if one exists. If there is no visit on which to anchor the Week 16 diary window, the Week 16 interval and its associated mean are defined as missing. If there are less than 4 non-missing assessments in the Week 16 diary window, the interval can be extended up to 7 additional days, one at a time, to obtain the most recent 4 non-missing values. The assessment of whether 4 non-missing values exist in the Week 16 diary window, and subsequent extension of that window, does not consider censored data in window construction (i.e., they are counted as non-missing unless they are truly unobserved). If the Week 16 diary window has less than 4 non-missing values after extending the Week 16 diary window up to a maximum of 14 days, the Week 16 diary window is defined as 7 days and the mean of the window is missing.

The lower bound of Week 15 diary window is defined as Day 99. The upper bound of the Week 15 diary window is the minimum of either Day 105 or the lower bound of the Week 16 diary window -1. Consequently, Week 15 may be less than 4 days if the Week 16 scheduled visit is before Day 112. Moreover, as Week 15 diary window cannot exceed 7 days, there could be daily assessments between Weeks 15 and 16 diary windows that do not fall into a diary window. If after constructing the diary windows, there are fewer than 4 non-missing values the mean for that particular window is missing and subject to imputation rules.

The postbaseline value of the actigraphy analyses will be analyzed similarly through Week 4 (Visit 5) or early discontinuation but will include time. Thus, Week 1 will be the mean of the 7 days of actigraphy events which has a start date and time occurring within 168 hours of the date and time of first study drug administration. The Week 2, Week 3 and Week 4 scores will be similarly defined. If there are less than 4 non-missing assessments occurring in at least 4 separate 24-hour increments, the weekly interval will be missing. Furthermore, as some analyses require use of the primary censoring rule, assessments collected on the day of rescue or afterwards will be excluded from the weekly visit interval calculation when implementing the rule for daily diary and actigraphy analyses. If, after exclusion of these records, there are less than 4 non-missing assessments, the weekly interval which implements the primary censoring rule will be missing. The post-study follow-up weekly score for daily diaries will be calculated as the mean of the 7 days prior to the follow-up visit which occur after last dose of study treatment.

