4.2. Secondary Objectives

4.2.1. Key Secondary Objectives

These are prespecified objectives that will be adjusted for multiplicity.

Objectives	Endpoints
To test the hypothesis that baricitinib 1-mg QD is superior to placebo in the treatment of patients with moderate to severe AD.	
 Proportion of patients achieving IGA of 0 or 1 with a ≥ 2-point improvement at Week 16
To compare the efficacy of baricitinib 1-mg QD, 2-mg QD, or 4-mg QD to placebo in AD during the 16-week double-blind placebo-controlled treatment period as measured by improvement in signs and symptoms of AD.	
 Proportion of patients achieving EASI75 at 16 weeks Proportion of patients achieving EASI90 at 16 weeks Percent change from baseline in EASI score at 16 weeks Proportion of patients achieving SCORAD75 at 16 weeks
To compare the efficacy of baricitinib 1-mg QD, 2-mg QD, or 4-mg QD to placebo in AD during the 16-week double-blind placebo-controlled treatment period as assessed by patient-reported outcome measures.	
 Proportions of patients achieving a 4-point improvement from baseline in Itch NRS at 1 week, 2 weeks, 4 weeks, and 16 weeks Mean change from baseline in the score of Item 2 of the ADSS at 1 week and 16 weeks Mean change from baseline in Skin Pain NRS at 16 weeks

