
Atopic Dermatitis Sleep Scale (ADSS)
	
The Atopic Dermatitis Sleep Scale (ADSS) is a 3-item, patient-administered questionnaire developed to assess the impact of itch on sleep including difficulty falling asleep, frequency of waking, and difficulty getting back to sleep last night. Patient's rate their difficulty falling asleep and difficulty getting back to sleep, items 1 and 3, respectively, using a 5-point Likert-type scale with response options ranging from 0 "not at all" to 4 "very difficult." Patients report their frequency of waking last night, item 2, by selecting the number of times they woke up each night, ranging from 0 to 29 times. The ADSS is designed to be completed each day with respondents thinking about sleep "last night." Each item is scored individually.
	
 ▪ Item 1 score of ADSS ▪ Item 2 score of ADSS ▪ Item 3 score of ADSS ▪ Change from baseline in score of Item 1 of ADSS ▪ Change from baseline in score of Item 2 of ADSS ▪ Change from baseline in score of Item 3 of ADSS 	
Single items: Item 1, range 0 to 4; Item 2, range 0 to 29; Item 3, range 0 to 4. Refer to Section 6.2.2 on how to derive the visit score.
 
Change from baseline: observed ADSS item score – baseline ADSS item score
	
Refer to Section 6.2.2 on how to derive the weekly visit score.
 
Missing if baseline or observed value is missing.

Measure	Description	Variable	Derivation / Comment	Imputation Approach if Missing Components
Patient-Oriented Eczema Measure (POEM)	The POEM is a simple, 7-item, patient-administered scale that assesses disease severity in children and adults. Patients respond to questions about the frequency of 7 symptoms (itching, sleep disturbance, bleeding, weeping/oozing, cracking, flaking, and dryness/roughness) over the last week. Response categories include “No days,” “1-2 days,” “3-4 days,” “5-6 days,” and “Every day” with corresponding scores of 0, 1, 2, 3, and 4, respectively. Scores range from 0-28 with higher total scores indicating greater disease severity (Charman et al. 2004).	POEM score	POEM total score: sum of questions 1 to 7, Range 0 to 28.	If a single question is left unanswered, then that question is scored as 0. If more than one question is unanswered, then the tool is not scored. If more than one response is selected, then the response with the highest score is used.

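### The Days 1–7 diary window admits a Day 1 sleep entry about the night before first dose, so the Week 1 ADSS Item 2 key secondary difference is 0 to 14.3% too small with a complete diary

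*SAP*

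**What the plan says.** SAP Section 6.2.2 builds postbaseline diary scores as weekly means: "Postbaseline daily diary endpoints will be the mean of weekly visit windows (diary windows) anchored on day of first dose (Day 1". The table that follows gives Week 1 as Days 1 to 7. For diaries, the baseline value "is the mean of the non-missing assessments in the 7 days prior to the date of first study drug administration", so Day 1 lies outside baseline and inside Week 1. If "there are fewer than 4 non-missing values the mean for that particular window is missing and subject to imputation rules", so a Week 1 mean rests on four to seven entries.

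The ADSS description is in Table JAHM.6.6 (Section 6.12): "The ADSS is designed to be completed each day with respondents thinking about sleep" during the previous night. For Item 2, "Patients report their frequency of waking last night, item 2, by selecting the number of times they woke up each night".

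One general sentence in Section 6.2.2 bears on whether a Day 1 entry counts: "Postbaseline measurements are collected after study drug administration through Week 16 (Visit 8) or early discontinuation visit". For actigraphy, the same section works to the clock, using "non-missing assessments in the 7 days prior to the date and time of first study drug administration". The diary rules use the date alone.

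Section 4.2.1 lists as a key secondary endpoint: "Mean change from baseline in the score of Item 2 of the ADSS at 1 week and 16 weeks". Section 6.6 carries the Week 1 version into the graphical procedure for all three doses (H4,11,0, H2,11,0 and H1,11,0). ADSS Items 1 and 3 at Week 1 are exploratory (Section 4.3) and share the window.

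**The concern.** A Week 1 sleep endpoint is there to show early onset. Because of the last-night recall, a Day 1 entry reports the night before any tablet was taken, whether the patient fills it in before or after dosing. Randomisation gives that night an expected treatment difference of zero. Averaging it with post-dose nights pulls the Week 1 difference towards zero.

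What is at stake is the size of the early-onset estimate for a multiplicity-controlled key secondary and, to a lesser degree, its power. The wording also leaves room for two programmers to keep different Day 1 entries. One could follow the Days 1–7 table and keep them all. The other could apply the general postbaseline sentence and drop those made before dosing.

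**Working it through.** The SAP gives no effect size, SD or power for ADSS Item 2 at Week 1, so there is no stated figure to reproduce.

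**Which night each entry describes.** Day 1 entry: the night before first dose. Day 2 to Day 7 entries: the first six nights after it. The general postbaseline sentence concerns when an entry is made, not which night it describes. A Day 1 entry made after dosing satisfies it and still reports a pre-dose night.

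**Dilution, complete diary.** Let D be the mean treatment difference over Days 2–7.
- Day 1 counted for everyone: (0 + 6D)/7 = 0.857D, a shrinkage of 1/7 = 14.3%, whatever the time course of effect over those six nights.
- Day 1 counted for a share q of patients: (1 − q/7)D.

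| q | Change in the difference |
|---|---|
| 0 | 0% |
| 0.25 | −3.6% |
| 0.5 | −7.1% |
| 0.75 | −10.7% |
| 1 | −14.3% |

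**Incomplete diary.** With q = 1, the shrinkage is the average weight of Day 1 in the weekly mean among patients with at least four entries (simulated, completion rates assumed):
- missingness equal across days, completion 50–90%: 0.143, that is 1/7;
- Day 1 always completed, other days 90%, 80% or 70%: 0.158, 0.176 or 0.192;
- Day 1 completed by 50%, other days 80–90%: 0.092–0.080.

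For one patient with four entries including Day 1 the weight is 1/4 = 25%. Section 6.2.2 also excludes diary entries from the day of rescue onward under the primary censoring rule. This removes later days of the week and raises the weight of Day 1 for those patients.

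**Power, illustration only.** Assumed SDs: between patients sb 1.5–3, day to day se 1–2, individual response sr 0–2. Test: two-sided 0.05 with a complete diary. Residual variance given the 7-day baseline mean is

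sb²(se²/7)/(sb² + se²/7) + f²·sr² + se²/n,

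with f = 6/7 and n = 7 where Day 1 is counted, and f = 1 and n = 6 where it is not.

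Example with sb = 2, se = 1.5, sr = 1:
- Days 2–7: 0.2975 + 1 + 0.375 = 1.6725, SD 1.293.
- Days 1–7, q = 1: 0.2975 + 0.7347 + 0.3214 = 1.3536, SD 1.163.
- Ratio of standardised effects: (6/7)(1.293/1.163) = 0.953.
- If Days 2–7 has 90% power, Days 1–7 has Φ(0.953 × 3.2415 − 1.96) = 87%.

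Over the whole grid, 90% for Days 2–7 becomes 88–90% at q = 0.25, 87–90% at q = 0.5 and 82–89% at q = 1. A simulated ANCOVA with 240 against 120 patients, sb = 2, se = 1.5 and q = 1 gave an estimate of 0.86 of the true difference for Days 1–7, against 1.00–1.01 for Days 2–7. Power was 0.82 / 0.88 / 0.90 against 0.90 / 0.91 / 0.91 for sr = 0 / 1 / 2.

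**Cost of dropping Day 1.** A patient loses the Week 1 mean only with exactly four entries, one of them Day 1. With independent daily completion p, the probability is p·C(6,3)·p³(1 − p)³ = 20p⁴(1 − p)³: 0.0020 at p = 0.95, 0.0131 at 0.90 and 0.0655 at 0.80.

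**The case against.** The best reply has four parts.

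1. The general sentence on postbaseline data stands in the same section as the table. Read together, they drop Day 1 entries made before dosing. If most patients fill in the sleep diary before their first tablet, q is near zero and so is the bias. Diary timing may well be in the protocol. This stands as a limit on size: the range must start at 0%. It does not remove the point, because entries made after dosing still describe a pre-dose night.
2. The Revision History lists both the interval-mean diary score and the use of time for actigraphy as Version 2 updates, so the contrast between them does not prove an oversight. That is fair. The dilution does not depend on the contrast.
3. The bias is conservative, both arms use the same window, and the Days 1–7 mean is what was prespecified. All true, and this limits the consequence. The endpoint would still understate the effect on the nights it is meant to measure.
4. Four of six entries is a stricter requirement than four of seven. In simulation at 80% completion, patients with a Week 1 mean fall from 96.7% to 90.1%. With q = 1 and a response SD of 2, Days 2–7 has about one point less power (84% against 85%). This stands: in that setting the gain is in the estimate only.

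A reader might infer that one seventh is a ceiling. It is not, as the uneven-completion weights show. A reader might also infer a power drop from 90% to about 79%. That figure holds the SD fixed and ignores the variance reduction from a seventh entry.

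**Conclusion.** The point holds. As the table is written, the Week 1 window admits an ADSS entry about the night before first dose, and nothing in the SAP removes such entries when they are made after dosing. With a complete diary, or missingness equal across days, the Week 1 Item 2 difference is 1 − q/7 of the Days 2–7 difference, so 0 to 14.3% smaller. The share q is not given. The average shrinkage can exceed one seventh if Day 1 is completed more often than later days or if rescue censoring removes later days. For a single patient with four entries it reaches 25%.

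The bias is towards no difference. It does not inflate type I error, and it does not touch the primary endpoint or any window from Week 2 onward. The power loss is modest and illustrative: the SDs are assumed, and the alpha reaching these hypotheses depends on a graph whose figure is not reproduced in the text at hand.

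A reader might carry the argument over to Week 1 Itch NRS. The SAP does not support that. Itch is rated as the worst in the past 24 hours, so a Day 1 itch entry may be wholly or partly pre-dose by an amount that cannot be worked out. No itch effect is claimed.

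**What to change.** Before unblinding:

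- Define the Week 1 window for ADSS Items 1–3 as Days 2–7, still requiring at least four non-missing entries.
- Keep Days 1–7 as a sensitivity analysis for Week 1 ADSS, and state there whether Day 1 entries made before dosing count.
- Leave all later windows and the main Itch NRS window as they are.

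The cost is one window definition and a few lines of SAP text. About 0.2%, 1.3% or 6.5% of patients lose their Week 1 ADSS mean at assumed independent daily completion of 95%, 90% or 80%. The MMRM treats these as missing and still uses the patients' later weekly means. They drop out of the Week 1 ANCOVA with mLOCF, because there is no earlier postbaseline value to carry forward. Week 1 would then mean different days for ADSS and for itch, which table footnotes should say. Since the main itch window does not change, no patient becomes an itch nonresponder through this edit.
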